### **3.3 The present project**

The present project is designed to prove that the thermoneutral conditions necessary for premature newborns to survive can be achieved by simple and low-cost equipment. The study aims to confirm its effectiveness already proven in laboratory tests in resource-limited conditions at Ola During Childrens Hospital. Currently lack of stable electric power supply severely hampers the use of conventional incubators at the hospital. The results of the study will demonstrate a possibility for premature newborns weighing around 1 to 2kg to be successfully treated, and therefore increased chance of survival in resource limited conditions. the study also aims to verify whether it is possible to train local staff to learn how to operate the incubator in a short time.

## **4 STUDY GOAL AND OBJECTIVES**

### **4.1 Objectives**

#### **4.1.1 Primary Objective**

- i .Verify the heat retention of a new incubator for premature babies

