#### 4.1.3 Primary Hypothesis

- i .New incubator keeps premature newborn temperature constant

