## 6. METHODS

### 6.1. Study parameters/endpoints

#### 6.1.1 Main study parameter

i . (Incubator) Measure the following parameters .(SpO2, HR, respiratory rate, Blood temperature, incubator inside temperature, incubator outside temperature, water temperature, incubator inside oxygen concentrate, milk intake, incubator inside humidity, incubator outside humidity)

	SpO2	HR	RR	BT(armpit)	incubator inside temperature	incubator outside temperature	water temperature	incubator inside oxygen concentrate	milk intake(ml)	incubator inside humidity	incubator outside humidity
pre implementation											
15 minutes											
30											
45											
60											
90											
120											
150											
180											
210											
240											
270											
300											
330											
360											

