#### 6.1.2 Procedure

1. Weigh neonate if weight is > 800 < 2000, and neonate has stable breathing document initial assessment and obtain informed consent from parent
2. Fill the plastic bottle with boiled water and put it in the incubator. We boil clean water by our electric kettle.
3. Assemble incubator
4. Place the bottle in the foil wrap and secure in designated position in the incubator at each end

5. Use hygrometer to confirm that internal incubator temperature is greater than 32 degrees Celsius and less than 37 degrees Celsius.
6. Place neonate inside incubator ensure they are stable.
7. Use data collection sheet to assess each parameter every **15 minutes for the 1st hour** if the baby is stable (maintain the baby's temperature and not change the breathing condition) , we measure the parameter **every 30 minutes**. If the temperature in the incubator exceeds 37° ,open the incubator for 5 minutes and measure the temperature again.
8. Newborn in the incubator always wear a pulse oximeter.
9. Measure without opening the incubator
10. We follow the ODCH doctor's instructions for the interval and methods of feeding.
11. Local nurses observes the newborn in an incubator for 24 hours and then return the newborns to cot.
12. Call a local medical doctor if the newborn has the following problems during our monitoring.: 1) the newborn's respiratory condition deteriorates, 2) the newborn has problem with their feeding patterns and vital signs.
13. Change the hot water to keep the newborn's temperature between 36.5°C and 37.2°C.
14. Wipe once a day with clean water. When replacing the newborn, disassemble the incubator and disinfect with alcohol.
15. measure the water temperature.

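### Water changes and incubator openings steer the recorded temperatures but have no place on the data sheet, so heat retention per fill cannot be reliably separated from staff correction

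*Protocol*

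**What the plan says.** The primary objective (Protocol 4.1.1) is to "Verify the heat retention of a new incubator for premature babies". The primary hypothesis (4.1.3) is "New incubator keeps premature newborn temperature constant", and the secondary hypothesis (4.1.4) concerns a constant temperature inside the incubator whatever the temperature outside.

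The procedure (6.1.2) includes two corrections made in response to temperature:

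- Step 13: "Change the hot water to keep the newborn's temperature between 36.5°C and 37.2°C". No interval, volume or count is given.
- Step 7: if the inside exceeds 37 °C, "open the incubator for 5 minutes and measure the temperature again".

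Readings are taken every 15 minutes in the first hour; then, for a stable infant, "we measure the parameter every 30 minutes". Step 11 keeps the infant in the incubator for 24 hours.

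The data sheet (6.1.1) has columns for SpO2, heart rate, respiratory rate and armpit temperature, followed by "incubator inside temperature, incubator outside temperature, water temperature, incubator inside oxygen concentrate, milk intake, incubator inside humidity, incubator outside humidity". Its rows run from before placement to 360 minutes.

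**The concern.** Heat retention is a property of the device between one heat input and the next. When staff return the infant's temperature to a target band on demand, a weaker device shows itself mainly by needing more corrections and less by a lower infant temperature. The number and timing of corrections are therefore part of the outcome, and the sheet does not ask for them.

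The secondary hypothesis is affected in the same way: openings under step 7 pull down high inside temperatures without a record that this was done.

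At stake is what can be concluded. An in-band record supports the statement that the incubator, with nurses refilling it, keeps infants in range. It does not say how long a fill lasts or how much refilling was needed. No later analysis plan can fully recover events that were never written down, and with about six infants expected there is little data to absorb the loss.

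**Working it through.** There is no sample-size or power figure to reproduce; six infants is an admissions forecast. The check compares the procedure with the sheet and then asks how far the recorded columns can stand in for the missing entries.

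**1. Procedure against sheet**

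| Event (6.1.2) | Direct entry on sheet (6.1.1) | Indirect trace |
|---|---|---|
| First fill, before placement (step 2) | none | water temperature in the row before placement, with no time of fill |
| Water change (step 13) | none | rise in "water temperature" between readings |
| 5-minute opening (step 7) | none | inside temperature above 37 °C, if a scheduled reading caught it |

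**2. Coverage.** The timed rows are 15, 30, 45 and 60 minutes, then every 30 minutes to 360: 4 + 10 = 14. Following step 7 over 24 hours gives 4 + (1440 − 60)/30 = 50 readings. So 50 − 14 = 36 readings, covering 18 of the 24 hours, have no printed row.

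**3. Expected events.** The hold times come from the protocol: over 3 hours per water change (6.3.2) and just over 150 minutes on the bench (Appendix, section 3). Fills = window ÷ hold time.

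| Window | 180 min per fill | 150 min per fill |
|---|---|---|
| 360 min | 2.0 fills, 1 change | 2.4 fills, so 3 started, 2 changes |
| 1440 min | 8.0 fills, 7 changes | 9.6 fills, so 10 started, 9 changes |

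On these figures, most changes fall after the last printed row.

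**4. Precision of the trace.** After the first hour, a change seen as a rise in water temperature lies somewhere in a 30-minute gap. The time between two such changes is then known only to within ±30 minutes: 30/150 = 20% of the bench figure, or 30/180 = 17% of the 3-hour figure. Two changes inside one gap look like one.

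**5. Illustration of direction only.** Assume a passive body that cools towards 25 °C at the Appendix bench rate (38 to 35 °C in 150 minutes) and is reset at once to 37.2 °C whenever it reaches 36.5 °C.

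- Time constant: 150 / ln(13/10) = 572 min.
- Time to cross the band: 572 × ln(12.2/11.5) = 34 min.

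| Retention | Corrections in 360 min | Mean of the 14 timed readings | Uncorrected value at 360 min |
|---|---|---|---|
| bench rate | 10 | 36.79 °C | 31.5 °C |
| half | 21 | 36.79 °C | 28.5 °C |
| quarter | 42 | 36.84 °C | 26.0 °C |

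The infant-temperature column barely moves while the number of corrections rises fourfold. In the lower two rows, corrections come 17 and 8 minutes apart. That is closer together than the 30-minute readings, so rises in water temperature could not count them. The model ignores the infant's own heat production and assumes instant correction, so it predicts no actual values.

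**The case against.** The best case on the other side has four parts.

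**Changing the water is normal use.** The bottles are a listed component, and the primary hypothesis and the summary's endpoint concern infant temperature in use. This stands: the data do bear on device plus nursing. But the stated objective is the device's heat retention, and even the in-use claim needs the number of changes behind it.

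**The sheet is not blind to corrections.** Bottles are filled with boiled water, so a refill should show as a clear rise, and a scheduled inside reading above 37 °C marks an opening. This largely stands. A reader might infer that a poor and a good device would leave the same record, or that very different refill rates could not be told apart. The documents do not support that. With a hypothetical change every 40 minutes and readings every 30, no gap contains two changes and each would show as a rise, so it could be told from one every 150 or 180 minutes. What is lost is timing, changes closer together than the readings, openings prompted between readings, and everything after 360 minutes unless rows are added.

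**No objective names a hold time.** This also stands. Section 3.3 speaks only of confirming laboratory effectiveness. It would be too strong to say the trial sets out to test 150 minutes or 3 hours, or that almost any device would pass: the summary itself foresees insufficient heat retention, and readings below 36.5 °C despite refilling would count against the device.

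**Other forms may exist.** Section 7.1.2 mentions paper checklists and case report forms that are not shown. If one of them logs these events, the point falls away, but nothing in the protocol asks for such a log.

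**Conclusion.** The point holds in a limited form. Device performance and staff correction are mixed in the recorded temperatures, and the plan collects only an indirect trace with which to separate them. That trace has a resolution of 15 to 30 minutes and printed space for 6 of the 24 hours. Heat retention per fill can be recovered only to about ±30 minutes after the first hour, and the first fill has no recorded time. The number of changes is recoverable when they are further apart than the readings, and the number of openings only in part.

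It would go too far to conclude that the readings say nothing about the device. They describe the device as nursed, and they would reveal one that fails despite refilling.

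The conclusion assumes that no undisclosed form logs these events. The event counts assume that the protocol's own hold times carry over to infants held in a 0.7 °C band (37.2 − 36.5). The bench test allowed a 3 °C fall (38 − 35), so changes could be more frequent. Nothing here bears on whether the band or the correction rules are right.

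**What to change.** **Recording.** Add time-stamped entries for each water fill or change (with water temperature before and after), incubator opened, and incubator closed. Include the first fill, and extend the printed rows to cover all 24 hours.

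**Reporting.** Give the number of changes and openings per infant beside the temperatures. Describe heat retention on the uncorrected intervals between fills, as the fall in inside and axillary temperature since the last fill.

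**Rules for a time-based summary:**

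- Start an interval only once the infant is within the protocol's band.
- Count only a fall below the protocol's own lower limit as loss of heat retention.
- Report readings above the upper limit separately as overheating.
- Treat a discretionary water change as the end of observation of that interval (censoring), not as device failure.

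Staff will tend to change water as the temperature falls, so this censoring is unlikely to be independent of the outcome. A time-to-event summary would tend to flatter the device and should be read together with the temperature falls and the number of changes.

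**Cost.** On the protocol's hold times, about 7 to 9 water-change entries per infant over 24 hours plus any openings, made by nurses already observing the infant, and a longer sheet. Care does not change. The entries must be in place before the first infant is enrolled, because they cannot be reconstructed afterwards.

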#### 4.1.2 Secondary Objectives

- i .Compare the temperature outside and inside the incubator

#### 4.1.3 Primary Hypothesis

- i .New incubator keeps premature newborn temperature constant

#### 4.1.4 Secondary hypothesis

- i .New incubator can maintain a constant room temperature regardless of the outside temperature

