#### **3.2 The importance of incubator**

Every hour, an estimated 340 babies die in the first week of birth, of preterm birth and asphyxia, which are the most frequently encountered causes for their deaths. Ninety-nine percent of these deaths occur in low- and middle-income countries(1). Compared with adults, newborns are particularly vulnerable to heat loss. Although passive, low-cost approaches such as the Embrace Infant Warmer are available to prevent heat loss of these newborn babes, they lack cooling functions and, therefore, it cannot control their , temperature(2). In many tropical countries, temperatures in the shade can reach >40 °C in the summer, and at this point, an incubator warmer can put babies at risk of hyperthermia. Advanced incubators exist, but they can cost thousands of dollars. The "Neonurture," a design that takes advantage of locally available replaceable parts of automobiles, is not a viable solution for mass production because it is still too complicate to be assembled and expensive (>\$1000) for "bottom of the pyramid" rural users(3). In addition to heat loss, nosocomial

infections are an important cause of infant morbidity and mortality in resource-poor countries, where neonatal deaths toll from sepsis reaches 29% of all neonatal deaths(4),(5). Preterm birth occurs in 11% of live births globally and accounts for 35% of all newborn deaths(6). Because preterm newborns have immature innate and adaptive immunity as compared with term babies, mortality due to inadequate immune system response is high in preterm newborns. Routine medical procedures including respiratory support carry an increased risk of infection and associated longterm morbidity in preterm infants(6). In addition, pediatric respiratory infections appear to contribute to some cases of sudden infant death syndrome(7). We are developing a thermodynamically advanced lowcost incubator suitable for operation in low-resource environments. The incubator features a modular design for multiple purposes. Primarily, it comprises of reusable control modules that have low maintenance requirements and low fixed costs. The incubator features four innovations:

- I. The new incubator is made of vinyl tubes and can be washed. it is reusable and easy to maintain. it can be used many times and is clean
- II. The incubator has a layer of air-contained tubes like a buoyancy ring and has been proven to have a high level of heat retention.

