### 1.1 Sample size calculation

During a week period all patients meeting the inclusion and exclusion criteria will be recruited. Based on current rates of admissions in the mentioned services, we expect to recruit at least 6 patients during a week data collection period.

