## **7.2 Statistical analysis**

This study only records biological parameters and temperature. If we get past neonatal mortality data at Ola During Children's Hospital , we compare the survival rates using Kaplan-Meier method.

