### 3. Performance test results

The results of the performance tests conducted for the warmer are as follows.

- Heat insulation capacity

Pour 2 liters of 38 Degree Celsius water, the average normal body temperature of neonates, into an aluminum can and place it inside of the warmer as a testing model of a neonate. Measure the core temperature of the testing model and count the time until it becomes lowered to 35 Degree Celsius, which is the temperature causing hypothermia, with an ambient temperature and humidity outside of the warmer set at 25 Degree Celsius and 50 % RH respectively. The measurement result is as shown below Figure 1.

[figure not shown]

Figure 1 – The test result obtained from the evaluation on the heat insulation capacity performed by the testing model of a neonate

From Figure 1, it was proven that this product was able to keep warming the testing model of a neonate for a little over 150 minutes with the temperature inside of the warmer being kept at 32 ~30 Degree Celsius during that period.

- Comparison between the core and back temperatures of the testing model  
Due to the nature of this product which supplies heat from under the mattress, the risk associated with the use is a potential scald on the surface skin of the back of a neonate, which the heat source has the closest contact with. To confirm safety, the back and core temperatures of the testing model of a neonate placed inside of the warmer were measured for comparison with an ambient temperature and humidity outside of the warmer set at 25 Degree Celsius and 50 % RH respectively. The measurement result is as shown below Figure 2.

[figure not shown]

Figure 2 – The test result obtained from the comparison made between the core and back temperatures of the testing model of a neonate

From Figure 2, it was proven that since the temperature applied to the back did not exceed the core temperature, there should be no risk of scald with this product.

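### The secondary objective compares inside with outside temperature, which does not name the quantity that would test the secondary hypothesis of constancy whatever the outside temperature

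*Protocol*

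**What the plan says.** Protocol 4.1.2 gives one secondary objective: "Compare the temperature outside and inside the incubator". Section 4.1.4 gives one secondary hypothesis: "New incubator can maintain a constant room temperature regardless of the outside temperature". I take room temperature there to mean the temperature inside the unit. Neither section gives limits for what counts as constant or a range of outside temperature.

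The data sheet in 6.1.1 records "incubator inside temperature, incubator outside temperature, water temperature" at each time point, with one row before the start and 14 rows from 15 to 360 minutes.

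Section 7.2 does not connect objective and hypothesis. It states: "This study only records biological parameters and temperature". The only method it names is Kaplan-Meier, for survival.

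Staff act on the inside temperature during use. Section 6.1.2, step 7: "If the temperature in the incubator exceeds 37° ,open the incubator for 5 minutes and measure the temperature again". Step 13 has the hot water changed according to the infant's own temperature.

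The Appendix bench test was run at one ambient setting, 25 °C, and reports "the temperature inside of the warmer being kept at 32 ~30 Degree Celsius" for a little over 150 minutes.

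The sample size section states: "we expect to recruit at least 6 patients during a week data collection period".

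**The concern.** A comparison of inside with outside temperature reads most naturally as asking whether one is higher. The hypothesis asks whether inside temperature stays put when outside temperature moves. A unit heated by hot water bottles will very probably be warmer than the ward, so finding it warmer says almost nothing about the hypothesis.

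Independence from ambient temperature is part of the case for the device. Section 3.2 faults an existing low-cost warmer for having no cooling function, and warns that in hot climates "an incubator warmer can put babies at risk of hyperthermia". The Appendix component list shows a hood, a mattress and hot water bottles and names no regulating part, although 3.2 mentions control modules. Whether the inside temperature follows a hot ward upwards is therefore open, and the objective as worded does not ask it. The risk is that a positive difference in level is later reported as support for 4.1.4.

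**Working it through.** The protocol gives no effect, SD, margin or test for this point, so there is no figure to reproduce. The check has four steps.

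**1. What a level difference can show.** Write inside = a + b × outside. The hypothesis concerns b (0 = independent, 1 = follows degree for degree). The mean difference is a + (b − 1) × mean outside, so very different values of b can give the same result. Take an assumed ward mean of 28 °C with readings at 26, 28 and 30 °C:

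| Outside (°C) | Follower, a = 5, b = 1 | Difference | Independent, a = 33, b = 0 | Difference |
|---|---|---|---|---|
| 26 | 31 | 5 | 33 | 7 |
| 28 | 33 | 5 | 33 | 5 |
| 30 | 35 | 5 | 33 | 3 |
| Mean | 33 | 5 | 33 | 5 |

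Both mean differences are 5 °C. Only the slope and the spread of the inside column differ.

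**2. What the bench test supplies.** At 25 °C ambient the offset was 32 − 25 = 7 °C falling to 30 − 25 = 5 °C. That shows an offset is realistic. It cannot show dependence on ambient, because ambient was fixed. The 2 °C fall is a change over time, which is why elapsed time belongs in any model.

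**3. Simulation, all inputs assumed except the layout.** Six infants (the expected minimum) with 14 post-start readings each (the sheet), giving 84 readings; ward mean 28 °C; ward SD 0.3, 1 or 2 °C, applied both between and within infants; reading noise SD 0.5 °C; 2000 runs. The level comparison is a paired t-test on per-infant mean differences, two-sided 0.05, counted when positive. No staff handling is simulated.

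| Device | Significant positive difference | Mean fitted slope |
|---|---|---|
| Follows ward, no offset | 2.4 to 2.8% | 1.00 |
| Follows ward, +2 °C | 100% | 1.00 |
| Follows ward, +5 °C | 100% | 1.00 |
| Independent, 5 °C above ward on average | 99.7 to 100% | 0.00 |

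The slopes of 1 and 0 were built in. The result is that the level comparison cannot tell the last three rows apart. Nor does it favour the independent device. At ward SD 2 °C, the follower's per-infant mean difference has SD 0.5/√14 = 0.134, so at +5 °C the t statistic is around 5/(0.134/√6) = 92. For the independent device the SD is √(4 + 4/14 + 0.25/14) = 2.07, so t is around 5/(2.07/√6) = 5.9.

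**4. How precise a slope could be.** With one intercept per infant, the standard error is about 0.5/(within-infant outside SD × √(84 − 6)). For SD 0.3 °C this is 0.5/(0.3 × 8.83) = 0.19, a 95% half-width of about 0.37. For SD 2 °C it is 0.5/(2 × 8.83) = 0.028, a half-width of about 0.06. Both assume independent errors. Serial correlation and adjustment for elapsed time would usually widen them.

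**The case against.** The strongest reply is that no faulty analysis has been planned. The objective names no statistic, 7.2 names no test or success rule for temperature, and comparing could as well mean comparing variation or plotting the paired series. Turning the objective into a statistic is normal work for an analysis plan, which is not shown. The paired readings are collected in any case, so nothing is lost.

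Most of this stands. The data are adequate, and no biased test can be attributed to the protocol. What does not go away is that objectives and hypotheses are protocol content, and here the objective does not identify what the hypothesis claims.

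A reader might infer that any device that simply follows the ward would be judged a success. The documents do not support that. There is no success rule, and a device with no offset shows a positive difference in under 3% of simulated runs. The problem arises only with a positive offset.

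A reader might also try to forecast how often the unit would be too hot or too cold. That is not supported either. The simulation leaves out opening the unit above 37° and changing the water. In addition, 32 °C appears only as a check before the infant is placed (6.1.2, step 5); of the two bounds in that check, only 37° recurs during use.

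Finally, the same staff handling can flatten the slope, so a slope near 0 would not prove that the device alone is independent. That is correct, and the fix says so.

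**Conclusion.** The point holds as a mismatch of wording and estimand. The secondary objective does not name the quantity that tests the secondary hypothesis. Read as a difference in level, it returns the same answer for a device following the ward with a positive offset as for one independent of the ward (100% against 99.7 to 100% of runs, under the assumed values). The bench test makes an offset of 5 to 7 °C plausible at 25 °C ambient but is silent on dependence.

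The conclusion rests on reading the objective as a level comparison, which is natural but not stated. It does not show that the device follows the ward. Separately, about 6 infants enrolled over a week at one hospital cannot support a claim about every outside temperature. The matter is modest: it is a secondary objective and needs no change to design or sample size.

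**What to change.** Reword 4.1.2 as estimating the dependence of inside temperature on simultaneous outside temperature, and report:

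- the slope with its confidence interval, from a model allowing for infant and elapsed time (time since the last water change, if recorded), together with the outside range observed;
- the within-infant variation of inside temperature, which addresses constancy;
- the share of readings above the protocol's own 37° in-use limit.

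Add two sentences. The first states that the result reflects the device together with staff handling (opening the unit, changing the water), so a slope near 0 is not evidence about the device alone. The second confines the conclusion to the outside temperatures observed during enrolment, and 4.1.4 should be narrowed to match.

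Cost: slightly more analysis on readings already on the sheet, plus one extra column if water-change times are to be recorded. The slope may be imprecise with about 6 infants and a narrow outside range; the interval will show this.
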